- Alcohol or drug abuse
- Received an analgesic within the last four hours
- History of congestive heart failure
- History of aortic or brain aneurysm
- Active Chest Pain
- Porphyria
- Active methadone treatment
- Pregnant or breastfeeding
- Signs of respiratory, hemodynamic, or neurologic compromise
 - Systolic blood pressure < 90 mmHg or > 180 mmHg
 - Heart rate < 50 beats per minute or > 150 beats per minute
 - Respiratory rate < 10 breaths per minute or > 30 breaths per minute
 - Glasgow Coma Score < 15
- Previously received ketamine ≤ 0.3 mg/kg IV for acute pain in the emergency department

VI. Recruitment Procedures

This is a single-center, prospective, randomized, double-blind, active controlled trial that will identify patients in the emergency department with acute pain who meet the eligibility criteria from January 2019 through January 2021 to achieve a sample of at least 180 patients.

VII. Definitions

Adequate pain relief:

- A score decrease on the Numerical Rating Scale (NRS) by ≥ 3 points

Moderate pain:

- A NRS score of 4-7 out of 10 per hospital policy

Severe pain:

- A NRS score of 8-10 out of 10 per hospital policy

Rescue analgesia:

- Any IV analgesic to be determined by the treating provider

Opioid tolerant:²⁵

- Patients receiving, for one week or longer, at least 60 mg oral morphine/day, 25 mcg transdermal fentanyl/hour, 30 mg oral oxycodone/day, 8 mg oral hydromorphone/day, 25 mg oral oxymorphone/day, or an equianalgesic dose of another opioid

VIII. Methodology

This is a single-center, prospective, randomized, double-blind, active-controlled trial. Patients who meet inclusion criteria and none of the exclusion criteria will be enrolled from January 2019 to January 2021 to achieve a goal sample size of 180 patients. Data such as demographics, self-reported pain score, adverse drug events, vital signs, and need for rescue analgesia within two hours of ketamine administration will be reported. Outcomes will include pain score reduction, incidence and severity of adverse drug events, adequate pain relief, and need for rescue analgesia within two hours of ketamine administration. All data will be entered in a password protected data sheet for proper analysis. No patient identifying data will be recorded.

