The administration of ketamine 0.1 – 0.3 mg/kg IV for acute pain in the Adult Emergency Department was approved at the September 2018 Pharmacy and Therapeutics Committee and is currently standard of care. Education was provided to all providers and nurses in the emergency department.

Patient screening, enrollment, and data collection will be performed by the treating resident or attending who will remain blinded. The Primary Investigator will also remain blinded and the ED pharmacists will be unblinded to facilitate ordering and delivery of the study drug.

Patients who consent to the study and meet eligibility criteria will be randomized to one of three doses of ketamine (0.1 mg/kg, 0.2 mg/kg, or 0.3 mg/kg) to be given IV infusion over 20 minutes. The block randomization list will be generated by the Hackensack Meridian Health Biostatistician prior to patient enrollment. Pharmacy investigators will maintain the randomization list and deliver the medication to the nurse in a blinded fashion. The medication will be prepared as a 0.1 mg/kg, 0.2 mg/kg, or 0.3 mg/kg dose in a 100 mL solution of dextrose 5% or sodium chloride 0.9% according to the predetermined randomization list. If there is a significant delay from the initial pain score to the study dose of ketamine administration, the patient will be withdrawn from the study and receive standard of care treatment. If pain is not controlled after the administration of ketamine, providers can order a rescue analgesic of their choice.

Patient history will be reviewed for known allergies, resuscitative equipment will be readily available, and the type and intensity of pain prior to administration will be documented. Baseline

vital signs, such as blood pressure, heart rate, and respiratory rate, will be assessed prior to IV administration of ketamine and at 120 minutes after infusion or upon discharge, whichever is sooner. The patient's self-reported pain score, need for rescue analgesia, and any adverse drug effects will be reassessed within 15 minutes from the end of the infusion and then every 30 minutes for up to 120 minutes or until discharge, whichever is sooner. Incidence, severity, and total number of adverse drug events will be documented using the Side Effects Rating Scale for Dissociative Anesthetics (SERSDA).

Procedure:

- Patient consent, screening, and enrollment will be performed by the treating resident or attending who will remain blinded
- Patient will be assigned a subject number

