- Treating resident or attending will notify the ED pharmacist that a patient has been enrolled in the trial
- ED pharmacist will notify the IV room and place the study drug order
- Either the ED pharmacist or a pharmacy supervisor will randomize the subject based on the predetermined randomization list
- Study drug will be prepared as 0.1 mg/kg, 0.2 mg/kg, or 0.3 mg/kg IV dose in a 100 mL solution of dextrose 5% or sodium chloride 0.9%
- ED pharmacist will promptly deliver the study drug to the ED
- Baseline vital signs will be assessed prior to starting the study drug infusion
- Study drug will be administered via IV infusion over 20 minutes
- Treating resident or attending will reassess the patient at 15 minutes from the end of infusion, at 30 minutes from the end of infusion, and then every 30 minutes for up to 120 minutes or until discharge, whichever is sooner

IX. Statistical Considerations

Randomization

The study participants will be randomly assigned into one of the three dose groups in the ratios of 1:1:1. Block randomization will be used to balance the sample size in each group.

Primary Outcome

The primary outcome is the numerical rating scale (NRS) pain score reduction from baseline to 120 minutes after the injection. The null hypothesis is that there is no difference among those three doses with respect to the mean score reduction.

Describing Data

The continuous variables (such as age of participant at the time of study) will be summarized using mean, median, standard deviation, interquartile range, range, minimum and maximum. The discrete variables (such as sex) will be summarized using frequency and percentage.

Exploring Differences

The two-sample Student's t-test will be used to compare the continuous variables between groups. If the normality assumption is violated, the Wilcoxon rank sum test will be used. The Shapiro-Wilk test will be used to evaluate the normality. The one-way analysis of variance (ANOVA) will be used to compare the continuous variables among groups. The Bartlett test will be used to evaluate the homogeneity of variances. The Tukey Honest Significant Differences test will be used to perform the multiple comparisons. If the normality assumption or homogeneity of variances assumption is violated, the Kruskal-Wallis one-way ANOVA by ranks will be used. The Dunn test will be used to perform the multiple comparisons.

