patient in each group, we will need to have 157 patients in each group. That is, a total of 471 patients (157 in each group) will be needed.

X. Discomfort and Risks

The risks of this study are minimal, as ketamine is currently the standard of care for acute pain in the Adult Emergency Department at Hackensack University Medical Center.

Side effects associated with ketamine are fatigue, dizziness, nausea, headache, feelings of unreality, changes in hearing, changes in vision, mood changes, generalized discomfort, and hallucinations.

Emergence reactions will be treated per hospital protocol with short active benzodiazepines. Midazolam 1 mg IV once (or 0.5 mg IV in the elderly) administered by the provider is typically sufficient, but doses may be repeated if necessary.

If there is a significant delay from the initial pain score to the study dose of ketamine, the patient will be withdrawn from the study and receive standard of care treatment. If pain is not controlled after the administration of ketamine, providers can order an IV analgesic of their choice as a rescue analgesic.

XI. Benefits

There will be no direct benefits to patients whose data is included in the analysis. The results of this study will help to better determine the ideal dose of intravenous ketamine for acute pain in the emergency department.

XII. Criteria for Evaluating Response

Specific patient information will be obtained from patients using a data collection form (Appendix A) and will include

- Demographics (age, sex, weight)
- Type of pain
- NRS pain rating
- Previous opioid usage
- Need for rescue analgesia
- Vital signs (heart rate, respiratory rate, blood pressure)
- Presence of side effects secondary to ketamine

XIII. Confidentiality

All study related materials will be kept confidential as required by law. Written documentation and computer files will remain in a locked or password protected location, with access given to those directly responsible for the conduct of the study. In addition, all information will be recorded in such a manner that subjects whose data is included in the analysis cannot be identified directly or through identifiers linked to the subjects. A data collection tool can be found at the end of this protocol (Appendix A).

XIV. Credentials, Training

All investigators have completed the Collaborative Institutional Training Initiative.

List of investigators

- [name], BCPS
- [name]
- [name], FACEP
- [name], DO
- [name]
- [name]

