CONTRAINDICATIONS

 • Hypersensitivity to ketamine • SBP > 180 and DBP > 100 mmHg • HR < 50 or > 150 bpm • Elevated intracranial pressure • Increased intraocular pressure • Pregnant or breastfeeding • Acute head or eye injury 	
 • Congestive heart failure - stage III and IV (myocardial depressant effects) • Aneurysm • Angina • Psychiatric disorders • Porphyria • Active methadone treatment
---	---

RELATIVE CONTRAINDICATIONS

- SBP <90 or > 140 mmHg
- Renal or hepatic insufficiency
- Alcohol or drug abuse
- Coronary artery disease

PRECAUTIONS

- Emergence reactions (vivid dreams, hallucinations, frank delirium, confusion, excitement, or irrational behavior) are dose-related but may occur at the subanesthetic doses used for treatment of acute pain
- Patients > 65 years old

DOSAGE AND ADMINISTRATION

1. Dosages:

- Single dose of 0.1 – 0.3 mg/kg/dose (maximum single dose: 30mg) administered over 20 minutes via intermittent infusion
 - Lower doses should be initiated for elderly patients or those with renal/hepatic dysfunction
 - Doses greater than 0.3 mg/kg/dose may lead to dissociative effects
- Dose may be repeated after 60 minutes up to a total cumulative dose of 0.3mg/kg or 30mg
- An additional dose may be repeated after 4 hours for patients requiring ongoing analgesia while remaining in the ED

2. Standard Dilution: Weight based dose diluted into 100 mL D5W or NS

TREATMENT OF EMERGENCE REACTION

- Emergence reaction may be treated with short acting benzodiazepines
- Midazolam 1mg IV once (0.5mg IV in the elderly) administered by the provider is typically sufficient
 - Doses may be repeated if necessary

DRUG INTERACTIONS

Ketamine is a substrate for CYP2B6, CYP2C9, & CYP3A4. The following includes, but is not limited to a list of drugs that may increase the levels/effects of ketamine.

- Sertraline, paroxetine (2B6)
- Fluconazole, nicardipine, NSAIDs, sulfonamides (2C9)
- Azole antifungals, clarithromycin, propofol, nicardipine (3A4)

ADVERSE REACTIONS

● Hypertension● Tachycardia/bradycardia● Tonic/clonic movements, tremor● Increased intracranial pressure● Emergence reaction/ dissociative effects (vivid dreams, hallucinations, frank delirium, confusion, excitement, or irrational behavior)	
● Visual disturbances (diplopia and nystagmus)● Nausea, vomiting● Skin rash● Headache● Fatigue
--	--

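### Rescue analgesia is not barred from being ketamine, so the two lower-dose arms could be topped up before the 120-minute score without the data form showing it

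*Combined protocol and SAP*

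**What the plan says.** Section VII (Definitions) defines rescue analgesia as "Any IV analgesic to be determined by the treating provider". Section VIII (Methodology) says "If pain is not controlled after the administration of ketamine, providers can order a rescue analgesic of their choice", and section X (Discomfort and Risks) says "providers can order an IV analgesic of their choice as a rescue analgesic". None of the three excludes ketamine. The only restriction on other ketamine is an eligibility criterion about earlier ketamine for pain in the emergency department (section V and Appendix A). It governs entry and says nothing about treatment after randomisation.

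Appendix B, the site's ketamine guideline, says under Dosage and Administration: "Dose may be repeated after 60 minutes up to a total cumulative dose of 0.3mg/kg or 30mg". Each dose runs over 20 minutes. A further dose is allowed after 4 hours.

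The primary outcome in section IX is the "pain score reduction from baseline to 120 minutes after the injection". The procedure list in section VIII has the provider "reassess the patient at 15 minutes from the end of infusion", with later checks up to 120 minutes or discharge. On rescue, section VIII says that "need for rescue analgesia within two hours of ketamine administration will be reported". The Appendix A form carries this as one yes/no row at 15, 30, 60, 90 and 120 minutes, with no entry for drug, dose or time. Section IX gives no rule for scores recorded after rescue.

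**The concern.** Ketamine dose is the randomised factor. Read together, the rescue rule and the appended guideline let that factor change after randomisation, and by more in the lower arms, because the guideline's ceiling equals the top arm's dose at 100 kg or less. A patient allocated 0.1 mg/kg could have had 0.3 mg/kg by the time of the primary score.

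Rescue with another drug also lowers later pain scores, but it leaves ketamine exposure at the allocated level. A ketamine repeat does not. Pain scores and side-effect ratings taken after it reflect a higher cumulative dose than the one they are analysed under. This matters in a study meant to describe both pain reduction and adverse effects by dose, and to inform a larger one. With only a yes/no entry, an analyst could not find these patients in the planned data, or set their late scores apart.

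**Working it through.** The plan gives no figure for repeat dosing, so there is none to reproduce. The check has three parts.

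**1. Room under the ceiling.** Inputs: allocated dose d = 0.1, 0.2 or 0.3 mg/kg (section VIII); cumulative ceiling 0.3 mg/kg or 30 mg (Appendix B). At 100 kg, 30 mg / 100 kg = 0.3 mg/kg, so at 100 kg or less the 0.3 mg/kg limit applies.

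Room = 0.3 − d. Largest exposure ratio = 0.3 / d.

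| Arm (mg/kg) | Room (mg/kg) | Largest cumulative dose / allocated dose |
|---|---|---|
| 0.1 | 0.3 − 0.1 = 0.2 | 0.3 / 0.1 = 3 |
| 0.2 | 0.3 − 0.2 = 0.1 | 0.3 / 0.2 = 1.5 |
| 0.3 | 0.3 − 0.3 = 0 | 0.3 / 0.3 = 1 |

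These are maxima. A same-dose repeat in the 0.1 arm gives (0.1 + 0.1) / 0.1 = 2. In the 0.2 arm a same-dose repeat would reach 0.4 mg/kg, above the ceiling, so only 0.1 mg/kg more is allowed and the ratio stays at 1.5. Above 100 kg the 30 mg limit shrinks the room. No figures are given there, because the protocol does not say whether Appendix B's 30 mg single-dose maximum also limits the study dose in the 0.3 arm.

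**2. Timing.** Section VIII times assessments from the end of the infusion. Appendix B does not say where its 60 minutes start. In minutes after the end of the first 20-minute infusion:

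- Counted from the end of infusion, the earliest repeat runs from 60 to 60 + 20 = 80. That is 90 − 80 = 10 minutes before the 90-minute rating and 120 − 80 = 40 before the 120-minute score.
- Counted from the start of infusion, it can begin at 60 − 20 = 40 and end at 60. That is at the 60-minute rating, 30 minutes before the 90-minute rating and 60 before the 120-minute score.
- If the primary score were instead timed from the start of infusion, it would fall at 120 − 20 = 100, still 20 minutes after a repeat ending at 80.

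On any of these readings a repeat can finish before the primary score, and the score then falls inside the 2 to 4 hour analgesic duration in Appendix B. The 15- and 30-minute ratings always come before a repeat. The separate 4-hour dose falls after the primary score and is not at issue.

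**3. What the records would show.** A repeat treated as rescue would give a Y in its interval, the same entry as any other IV analgesic. Staff who regarded it as ordinary guideline dosing might not enter it at all. The medical record may identify the drug, but the protocol plans no such capture.

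On control of the ceiling, the ordering provider is blinded and cannot know the remaining room. Section VIII says "the ED pharmacists will be unblinded to facilitate ordering and delivery of the study drug", so the pharmacist could apply it, but no section assigns that task. At 100 kg or less, a refusal on these grounds would point to the 0.3 mg/kg arm.

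**The case against.** The strongest reply is that the route is inferred. The body of the protocol uses Appendix B as the site's approved guideline and as the basis for the exclusions, not as a study dosing rule. Section VIII gives one randomised dose and then speaks of rescue, which most naturally suggests a different drug. The entry exclusion for earlier ketamine fits a single intended exposure, and a provider blinded to dose would find a repeat awkward to order. Free choice of rescue is also a defensible care decision. All of this stands as a reason to expect few repeats. It does not close the gap: the natural reading is not written down, the guideline describes current care on which staff were trained, and enrolment requires that the provider judged IV ketamine to be needed.

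A reader might go further and infer that repeats would cost the trial power, which barring ketamine would recover. The documents do not support this. They give no rate of repeat dosing, and patients denied ketamine would presumably get another IV analgesic, which also lowers the 120-minute score. Suppose, for illustration, that the protocol's example of 1.25 points per dose step is linear in dose. A 0.2 mg/kg top-up in the 0.1 arm is then worth 2 × 1.25 = 2.5 points. Another analgesic worth an assumed 2.5 points, given to the same share of patients, would move that arm's mean by the same amount. The lack of a general rule for scores after any rescue is a separate matter. This trial is also described as exploratory, with 60 per group not derived from a power calculation.

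Nor should the point be read as saying that repeats are planned or have occurred.

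**Conclusion.** The point holds as a minor one. The written rules permit further ketamine before the 120-minute score in the two lower arms but not in the 0.3 mg/kg arm, and the planned data would not identify it. In a re-dosed patient at 100 kg or less, cumulative ketamine could reach 3 times the allocated dose in the 0.1 arm and 1.5 times in the 0.2 arm. The harm specific to ketamine is attribution: late pain scores and side-effect ratings would be credited to a dose lower than the one received.

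This rests on three conditions: that providers regard the Appendix B repeat as open to them for enrolled patients, that some use it, and, for the quoted ratios, that the ceiling is filled. How many patients would be affected cannot be estimated from the documents. Early ratings are untouched.

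**What to change.** State in sections VII, VIII and X that, for enrolled patients in all arms, rescue means any IV analgesic other than ketamine until the 120-minute assessment or discharge, and that this overrides the 60-minute repeat in Appendix B. The sponsor's clinicians should confirm that this is acceptable. Add rescue drug, dose and time to the Appendix A form beside the existing yes/no row. In section IX, provide that pain and side-effect scores recorded after any further ketamine are flagged in the dose comparison.

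The cost is one sentence in three sections, one form entry and one analysis flag. The downside is slightly less provider discretion for two hours and possibly somewhat more opioid rescue, in a trial motivated by alternatives to opioids. If the clinicians prefer to keep ketamine available, the form entry and the flag are still worth having, since they would make any repeat visible.
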